### **3.3 DOSE ESCALATION**

Dose escalation will proceed in cohorts of 3 to 6 patients. Patients will not begin treatment at the next higher dose level until all patients treated at the previous dose level have reached day 21 of the protocol, recovered from any clinical or laboratory toxicities and would be able to initiate another cycle of treatment unless restaging has demonstrated progression of their disease). The MTD is the dose level at which no more than 1 of up to 6 patients experience DLT, and the dose below that at which at least 2 (of  $\leq$  6) patients have DLT as a result of the drug. If a patient did not experience DLT and did not finish 1 cycle of treatment (42 days), he or she will not be evaluable for determination of the MTD and will be replaced in the dose level.

Dose escalation will follow the rules outlined in the Table below.

Number of Patients with DLT at a Given Dose Level	Escalation Decision Rule
0 out of 3	Enter up to 3 patients at the next dose level
$\geq 2$	Dose escalation will be stopped. This dose level will be declared the maximally administered dose (highest dose administered). Up to 3 additional patients will be entered at the next lowest dose level if only 3 patients were treated previously at that dose.
1 out of 3	Enter up to 3 more patients at this dose level. 

• If 0 of these 3 patients experience DLT, proceed to the next dose level.

• If 1 or more of this group suffer DLT, then dose escalation is stopped, and this dose is declared the maximally administered dose. Up to 3 additional patients will be entered at the next lowest dose level if only 3 patients were treated previously at that dose.

$\leq 1$ out of 6 at highest dose level below the maximally administered dose	This is the MTD and is generally the recommended phase 2 dose. At least 6 patients must be entered at the recommended phase 2 dose.

The MTD has already been defined for patients treated with the 10-day regimen. For patients treated with the 5-day regimen dose escalation will continue through the 5 mcg/kg/day dose level in the absence of  $\geq 2$  DLTs for the patients treated for any of the dose levels being evaluated for the 5-day regimen. If an MTD is not identified up to 9 patients may be treated at the maximum administered dose (MAD) of 5 mcg/kg/day to better evaluate the therapeutic potential of rhIL-15 given by this schedule.

### **3.4 DRUG ADMINISTRATION**

For all dose levels, the dose of rhIL-15 will be diluted in the appropriate volume of 0.1% human serum albumin (HSA) in 5% dextrose in water, USP (D5W) to reach a final rhIL-15 concentration of 1 mcg/mL. The rhIL-15 treatment will be administered to the patient by continuous 24-hour intravenous infusion (CIV) using portable ambulatory pump on the inpatient unit for either a total of 240 or 120 hours depending on the treatment cohort. Treatment with rhIL-15 will begin within 4 hours of preparation of the infusion bag and each infusion bag must be completed within 24 hours from the time drug administration begins. If the infusion bag is not empty at the 24-hour time point, the remaining solution will be discarded and the next infusion bag will be started. **The 240- or 120-hour infusion time frame will not be extended.**

The rhIL-15 infusion solution is stable at a concentration of 1 mcg/mL with 0.1% HSA for 4 hours at controlled room temperature (15°C–30°C) prior to initiation of the 24-hour infusion or 24 hours at 2-8° C prior to initiation of the 24-hour infusion. This stability information was previously documented by the Biopharmaceutical Development Program (BDP) of Leidos Biomedical Research, Inc.-Frederick, the drug manufacturer.

The rhIL-15 will be infused through a PICC or another appropriate CVAD.

Samples for PK assessments must **not** be drawn from the PICC or CVAD through which the rhIL-15 is infused. If feasible, venous access will be placed at 2 locations **NOT in the same extremity** during cycle 1. This will prevent contamination of the blood draws with residual rhIL-15 present in the catheter or double lumen catheters with distal openings in close proximity.

In Cycle 2 and beyond, the IL-15 infusion may be put on hold for 5-15 mins to collect routine (non-PK) daily labs.

### **3.5 DOSE MODIFICATIONS**

Since this is a phase I study intending to define the MTD, there will be no dose modifications or interruption of treatment during the first cycle of treatment for the 5-day dosing cohorts. **The rhIL-15 infusion maybe interrupted for up to 24 consecutive hours for reasons other than DLTs without bearing on the patient's continued treatment during subsequent treatment cycles for patients treated with either schedule. Interruptions of the infusion will not be made up by extending the 240- or 120-hour infusion and there will be no change in the date and time the 10- or 5-day infusion is terminated unless the treatment is stopped early for safety reasons.** Patients with evidence of clinical benefit at restaging may have interruptions or early termination of their CIV rhIL-15 during later retreatment cycles for non-DLT events to improve tolerability of the treatment without forfeiting the possibility of subsequent treatment cycles. Stoppage of less than 15 minutes occurring during the daily change of the rhIL-15 infusion device will not be considered an interruption.

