### Design:

- This is a single-institution, open-label, non-randomized 3 + 3 design phase I dose-escalation study.
- Groups of 3 to 6 subjects will receive CIV rhIL-15 at doses of 0.1, 0.25, 0.5, 1, 2, and 4 mcg/kg/day for 10 days provided that DLT has not been observed.

**Abbreviated Title:** *Ph I Study of CIV rhIL-15*

**Version Date:** 06/13/2018

- After assessments of the 10-day dosing cohorts have been completed, new groups of 3 to 6 subjects will receive CIVrhIL-15 at doses of 3, 4 and 5 mcg/kg/day for 5 days provided that a DLT has not been observed.
- Patients with evidence of response and the absence of significant toxicities will be eligible for repeat cycles of treatment.
- Samples for correlative studies will be obtained prior to treatment and at specific times points during and after treatment to assess pharmacokinetics of rhIL-15, the effect of rhIL-15 on immune cell subset populations and pro-inflammatory cytokine levels in the peripheral blood and for the development of neutralizing anti-rhIL-15 antibodies.

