#### **3.10.1 Off-Treatment Criteria**

- DLT as defined in Section [3.2](#).
- Persistent (> 14 days) treatment-related grade 2 (non-DLT) adverse events.
- Completion of protocol therapy
- Patient requests to be withdrawn from active therapy.
- Disease progression.
- No evidence of clinical response (i.e., patient has stable disease) on radiographic restaging after 2 consecutive cycles of treatment.
- The detection of anti-IL-15 neutralizing antibody serum titer  $\geq 500$  ng/mL as described in [APPENDIX C](#) prior to subsequent treatment cycles.
- Evidence the patient has developed auto-immunity that involves a vital organ (heart, kidney, brain, eye, thyroid or adrenal gland, colon, lung). Patients who develop new auto-antibodies without clinical evidence of end organ dysfunction will be seen by the appropriate Internal Medicine subspecialists to assess their risk for developing an autoimmune syndrome.
- Interruption of CIV rhIL-15 treatment for any reason for more than 24 consecutive hours during cycle 1. Stoppage of less than 15 minutes occurring during the daily change of the rhIL-15 infusion device will not be considered an interruption.
- Positive pregnancy test

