The MTD for each schedule will be based on the assessment of DLT during the first cycle of treatment, and will be defined as the dose level at which less than one-third of patients (0/3 or 0-1/6 patients) treated at that dose experience a DLT, with the next higher dose level demonstrating a one-third or greater number of patients ( $\geq 2/3$  or  $\geq 2/6$  patients) having DLT. If a patient did not experience DLT and did not finish 1 cycle of treatment (either 42 or 21 days), he or she will not be evaluable for determination of the MTD and will be replaced in the dose level. An additional 3 to 6 patients will be enrolled at the MTD or, if no severe or dose-limiting toxicities are encountered, the maximum administered dose of rhIL-15, so that a total of 9 patients will potentially be treated at MTD for either schedule to better characterize the clinical activity of

CIV rhIL-15 in this patient population. If feasible, the patients enrolled in this expansion cohort will be limited to histologic cancer subtypes previously shown to be sensitive to immunotherapy (renal cell carcinoma, melanoma, prostate, colorectal and ovarian cancer).

As of April 2016, twenty-four evaluable patients have enrolled on Dose Levels 1-6; with 2 more to be enrolled in Dose Level 6 after Amendment G. A maximum of 6 evaluable patients may be enrolled at DL 7 & 8 with an additional 9 at DL 9. If all dose levels are evaluated (with 6 patients per remaining dose levels and 9 total patients at the MTD or maximum administered dose), a maximum of 47 evaluable patients will be enrolled. An additional 5 patients may be enrolled to compensate for inevaluable patients; thus, bringing the maximum accrual ceiling to 52.

Similarly, if all dose levels are evaluated, the minimum number of patients required will be 41 (24 evaluable patients have enrolled at DL 1-6; with 2 more to be enrolled in Dose Level 6 after Amendment G and with 3 patients enrolled at DL 7 & 8; 9 at DL 9; and 5 inevaluable patients a minimum of 46 will be reached).

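### For the 5-day cohorts, Sections 3.5 and 3.10.1 leave cycle 1 interruptions unreconciled, and MTD evaluability sets no minimum delivered dose, so an under-dosed DLT-free patient can count in full

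*Combined protocol and SAP*

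**What the plan says.** **Conduct.** Section 3.5 gives the aim of defining the MTD as its reason and states that "there will be no dose modifications or interruption of treatment during the first cycle of treatment for the 5-day dosing cohorts". Its next sentence, which covers patients on either schedule, lets the infusion be interrupted "for up to 24 consecutive hours for reasons other than DLTs without bearing on the patient's continued treatment during subsequent treatment cycles". The closing phrase about subsequent cycles can limit either when the interruption may happen or which later treatment is unaffected, so the cycle covered is unclear.

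**Removal.** Section 3.10.1 lists as an off-treatment criterion: "Interruption of CIV rhIL-15 treatment for any reason for more than 24 consecutive hours during cycle 1". No schedule is named, and separate shorter stops are not added together.

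**Lost dose.** Section 3.5 adds: "Interruptions of the infusion will not be made up by extending the 240- or 120-hour infusion". Section 3.4 says: "If the infusion bag is not empty at the 24-hour time point, the remaining solution will be discarded".

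**Evaluability.** Section 8 sets the replacement rule: "If a patient did not experience DLT and did not finish 1 cycle of treatment (either 42 or 21 days"), the patient is not evaluable for the MTD and is replaced. Section 3.3 has the same rule with 42 days only. Neither section mentions the amount of drug received.

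**The concern.** A 3+3 decision rests on three or six patients, each taken to carry the DLT risk of the assigned dose. If a patient received clearly less than that dose, had no DLT and still counts as a full observation, the level may look safer than it is.

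The 5-day cohorts are exposed to this because their levels lie close together and the infusion is short, so one day lost is a fifth of the cycle 1 dose. The Schema states that the 5-day MTD has not yet been identified. Section 3.3 allows up to nine patients at 5 mcg/kg/day if no MTD is found.

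**Working it through.** **Inputs.** The 5-day cohorts are treated "at doses of 3, 4 and 5 mcg/kg/day for 5 days" (Précis, Design). The infusion runs "for either a total of 240 or 120 hours depending on the treatment cohort" (Section 3.4). The single-stop threshold is 24 hours (Section 3.10.1), with no make-up (Section 3.5).

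**Step 1: the plan's own table.** Section 8 gives the probability of escalating as .91, .71, .49, .31, .17 and .08 for true DLT rates of 10% to 60%. With P = (1−p)³ + 3p(1−p)²·(1−p)³, the results are .906, .709, .494, .309, .172 and .082. The table is correct, given that every counted patient has risk p.

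**Step 2: dose delivered on the 5-day schedule.** Delivered dose = daily dose × (120 − hours missed)/24. One 24-hour stop removes 24/120 = 20%.

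| Level (mcg/kg/day) | Planned total (mcg/kg) | After one 24-h stop | Planned total one level below | Hours missed for equality |
|---|---|---|---|---|
| 3 | 15 | 12 | none | – |
| 4 | 20 | 16 | 15 | 120 × (1 − 3/4) = 30 |
| 5 | 25 | 20 | 20 | 120 × (1 − 4/5) = 24 |

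A single stop that does not trigger removal reaches equality only at 5 versus 4 mcg/kg/day. At 4 mcg/kg/day, equality needs 30 hours in at least two stops, which no cumulative limit prevents. Two 24-hour stops would remove 48/120 = 40%.

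**Step 3: the 10-day schedule for comparison.** A 24-hour stop removes 24/240 = 10%. At 4 mcg/kg/day it leaves 36 mcg/kg, against 20 planned at 2 mcg/kg/day. Equality would need 120 hours or more at every level. The bar in Section 3.5 names only the 5-day cohorts, and the 10-day MTD is already set, so the point is confined to the 5-day schedule.

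**Step 4: possible effect on a decision (illustration).** The documents give neither DLT rates by dose nor an interruption frequency. Assume that DLT risk follows total dose entirely, so that an under-dosed patient carries the lower level's rate. Take one such patient, in the first three only. With true rates of 50% at the full dose and 30% at the level below:

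- No DLT in three: 0.7 × 0.5 × 0.5 = .175.
- Exactly one DLT in three: 0.3 × 0.25 + 2 × (0.5 × 0.7 × 0.5) = .425.
- Clearing: .175 + .425 × 0.5³ = .228, against .172 with full dosing.

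| Rate at full dose / level below | All fully dosed | One under-dosed patient in the first three |
|---|---|---|
| 50% / 30% | .172 | .228 |
| 50% / 20% | .172 | .256 |
| 40% / 30% | .309 | .348 |
| 30% / 20% | .494 | .541 |

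If risk follows infusion rate alone and does not depend on duration, the last column equals the one before it.

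**The case against.** **The two sections can coexist.** Section 3.5 can be read as the conduct rule and Section 3.10.1 as a trial-wide removal list that still serves the 10-day cohorts. A reader might infer that 3.10.1 permits cycle 1 stops of up to 24 hours. It does not say so, and tolerance of shorter stops is only an implication. Section 3.10.1 also keeps a two-cycle response criterion, although Section 3.1 gives 5-day patients four cycles, which suggests text not updated for the shorter schedule. This softens the conflict, but no passage states the reading that removes it.

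**An interruption would be noticed.** Under Section 3.5 it would be a deviation, reportable under Section 7.2.1, and the team meets weekly (Section 7.4.1). That is fair, but neither section says how the patient counts toward the MTD. The gap remains even if 3.5 governs, because a barred interruption can still happen.

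**Finishing a cycle of treatment may imply receiving it.** This is a possible reading, but the only measure given is days.

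**Equal total dose is not equal exposure.** This stands. An interrupted patient at 5 mcg/kg/day still has 96 hours at a rate 25% above the level below. Section 1.2.1.4 reports a half-life of about 2½ hours after bolus dosing, with toxicity timed to each infusion. Against that, Section 1.2.1.3 describes macaque effects under continuous infusion as most notable from day 7, which suggests that duration matters. The documents do not settle it.

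**A stop forced by drug toxicity is often already a DLT.** This also stands, subject to the exceptions in Section 3.2.1. It leaves mainly stops for other reasons.

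**Conclusion.** The point holds for the 5-day cohorts, with moderate confidence. The cycle 1 interruption passages need reconciling. As written, the evaluability rule can count in full a DLT-free patient who lost 20% of the planned cycle 1 dose in one stop, or more over repeated stops.

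Two stronger conclusions are tempting but unsupported. The first is that an under-dosed patient generally clears a level on the lower level's dose. After one 24-hour stop, the totals coincide only at 5 versus 4 mcg/kg/day. That is the top level, where clearing means supporting 5 mcg/kg/day as the MTD or maximum administered dose, since there is no further escalation. At 4 mcg/kg/day the patient still gets 16 mcg/kg, against 15 at the level below. The second is that the MTD will be too high. That needs interruptions to occur and DLT risk to depend at least partly on total exposure, and the documents establish neither. Under those assumptions the direction is toward clearing the level. In the cases shown, one such patient raises the chance by about .04 to .08.

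The gap does not invalidate the 3+3 design. It should be closed before a 5-day MTD is declared.

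**What to change.** 1. Reconcile Section 3.5, including its ambiguous 24-hour sentence, with Section 3.10.1 for the 5-day cohorts. Which clinical rule applies is for the sponsor to decide.
2. In Sections 3.3 and 8, state that a DLT-free patient who received less than a minimum cumulative fraction of the planned cycle 1 dose is not evaluable for the MTD and is replaced. The sponsor sets the fraction in advance. Patients with a DLT already remain evaluable under both sections, so that part needs no change.
3. Report delivered mcg/kg in cycle 1 for each patient, by dose level.

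The cost is protocol wording and an occasional replacement, drawn from the five patients that Section 8 already allows for inevaluable cases. Replacing under-dosed DLT-free patients while always keeping those with a DLT leans slightly toward caution, as the existing replacement rule already does.

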### **3.6 MONITORING DURING THERAPY**

The following tests and procedures will be performed during all treatment cycles as indicated in Section **3.8**, Study Calendars.

- 3.6.1 Acute Care, Hepatic and Mineral Panels, ammonia level and LDH
- 3.6.2 CBC with differential
- 3.6.3 Troponin T or I, based on availability of test in DLM
- 3.6.4 ANA, RF, anti-thyroid antibody and thyroid function tests: TSH and T4
- 3.6.5 EKG
- 3.6.6 Percutaneously Inserted Central Catheter (PICC) or another appropriate central vascular access device (CVAD) will be inserted from Day -7 to Day 1 of each treatment cycle for infusion of rhIL-15. An additional PICC, CVAD or a peripheral venous catheter may be inserted and used for drawing multiple blood samples as needed. Samples for PK assessments must **not** be drawn from the CVAD through which the rhIL-15 is infused.
- 3.6.7 Radiographic Evaluation and Laboratory Assessments for Clinical Responses
- 3.6.8 Other Studies

Patients may have additional laboratory or radiological studies performed as clinically indicated, in particular if there were a suspicion of disease progression that would warrant an urgent therapeutic intervention.

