### 3.8.2 5 Day Schedule

Procedure	Pre-treatment		Days During-treatment 							After treatment			
	Screening	Baseline 	1	2	3	4	5	6	8	21±4 	End of Treatment 	Follow-Up Period 	End of Study 
CIV rhIL-15 treatment 			x	x	x	x	x	x 					
Pathology confirmed	x												
Performance status	x	x	x						x		x	x	x
History & physical exam 	x	x	x	x	x	x	x	x	x		x	x	x
Vital Signs  and Weight	x	x	x	x	x	x	x	x	x		x	x	x
NIH Advance Directives Form 													
Acute Care, Hepatic and Mineral Panels and LDH	x	x	x	x	x	x	x	x	x	x	x	x	x
Ammonia level	x		x						x				
I/Os			x	x	x	x	x	x	x				
CBC w/differential	x	x	x	x	x	x	x	x	x	x	x	x	x
Reticulocyte Count		x											
Hepatitis and HIV serology	x												
Thyroid function tests: TSH and T4	x									x	x		
Troponin T or I, based on availability of test in DLM		x	x										
Urinalysis	x												
EKG	x		x										
Pulmonary function tests	x												
HLA (A, B, C, DR, DQ) typing		x											
Tumor imaging and serum tumor markers 	x	x									x		
Serum βHCG 	x		x										
ANA, RF and anti-thyroid antibodies	x										x		
Pharmacokinetics (PK) 			x	x	x	x	x	x					
Serum immunoglobulin levels		x											
Flow cytometry ([name] Lab) 		x	x						x	x			
Flow cytometry ([name] Lab) 		x	x						x	x			
Cytokine and MesoScale inflammatory cytokines 			x	x	x	x	x	x	x	x			
Anti-IL-15 antibodies 			x							x		x	
Optional Tumor Biopsies 		x							x				

**Abbreviated Title:** Ph I Study of CIV rhIL-15

**Version Date:** 06/13/2018

1. All cycles are 21 days in length, but the end of cycle evaluations may be performed  $\pm$  4 days from this time point and an additional 7 days allowed for reasons other than recovery for treatment-related toxicities. Cycle 1 day 21 and cycle 2 day 1 maybe the same calendar day for certain patients. This also applies to later cycles where day 21 of a previous cycle falls on the same calendar day as day 1 of the subsequent cycle.
2. Patients whose best response after 4 consecutive cycles of treatment is stable disease will be followed with routine exams and restaging scans: Every 60 days x 3; then quarterly for up to 2 years after starting treatment unless progressive disease is documented, or they begin another treatment for their cancer.

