3. Denotes testing to be performed at an end of study visit (just prior to the patient being taken off study), if feasible.
4. Because the treatment is CIV for 120 hours, the day 5 treatment concludes on day 6.
5. Interval history during inpatient treatment period.
6. Vital signs, including heart rate, blood pressure, respiration, temperature and arterial oxygen saturation (SO2) by transcutaneous pulse oximeter.
  - a. Every 4 hours  $\pm$  1 hour during treatment days 1 through 6 (SO2 every 8 hours  $\pm$  1 hour)
  - b. Every 8 hours  $\pm$  1 hour on other inpatient days
  - c. Once at outpatient clinic follow-up visits on days 8 and 21.
  - d. Off treatment visit
  - e. End of study visit.
7. Repeat radiologic studies to assess response the last week (day 14 through 21) of even numbered cycles (2, 4, 6 and so on) as long as patients meet criteria to continue treatment. Patients with evidence of a partial or complete response (RECIST criteria) may undergo a confirmatory scan at least 4 weeks after the scan which first met the criteria for a clinical response. Patients with tumors known to have tumor markers (PSA, CEA, and CA125) will have the serum level of these markers assessed at the time of their radiographic restaging.
8. Pretreatment on Day 1 or within 3 days of starting treatment in women of child bearing potential.
9. PKs are collected on Cycle 1 only. Samples are collected in 4 mL SST tubes at the time points. These samples will be held at room temperature until picked up by the [name] laboratory (Blood Processing Core) for processing ([contact] for pickup). See Section [5.1](#) for additional details.
10. One 10 mL lavender-top tube will be drawn for Lymphocyte Phenotype IL-15 FACS analysis. If the Immunology Section Laboratory is unable to perform this analysis on the specified days, this assessment maybe omitted or replaced with standard TBNK panel. See Section [5.1.2](#) for additional details:
  - a. At baseline (need to perform twice before initiating study drug if at all possible.)
  - b. Day 1: prior to the start of the CIV rhIL-15 infusion
  - c. Days 8 and 21 drawn with the routine laboratories
11. Two 10 mL lavender-top tubes will be drawn for the [name] Lab (NIAID) to perform special FACS analysis. See Section [5.1.2](#) for additional details:
  - a. At baseline (need to perform twice before initiating study drug if at all possible.)
  - b. Day 1: prior to the start of the CIV rhIL-15 infusion

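### The 5-day calendar schedules no auto-antibody test between cycles, so the Section 3.10.1 referral for new auto-antibodies is delayed until treatment has ended

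*Combined protocol and SAP*

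**What the plan says.** Section 3.6 opens with "The following tests and procedures will be performed during all treatment cycles as indicated in Section" 3.8, and its fourth item is "3.6.4 ANA, RF, anti-thyroid antibody and thyroid function tests: TSH and T4". The list names the tests and leaves their timing to the calendars.

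In the 5-day calendar (3.8.2), the row "ANA, RF and anti-thyroid antibodies" is marked at Screening and at End of Treatment only. It has no footnote. Footnote 16 puts the End of Treatment visit about 30 days after the last dose. The row "Thyroid function tests: TSH and T4" is marked at Screening, 21±4 and End of Treatment.

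In the 10-day calendar (3.8.1), the auto-antibody row and the thyroid row are both marked at Screening and at days 28-34, which lie within the cycle.

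Section 3.10.1 makes autoimmunity involving a vital organ a reason to stop treatment. It separately sends patients with new auto-antibodies but no clinical organ dysfunction to a subspecialist, who assesses their risk of an autoimmune syndrome.

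**The concern.** Items on the same 3.6.4 line are scheduled differently in the 5-day calendar, and the auto-antibody panel is scheduled differently in the two calendars. I found no reason given for either difference.

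The 3.10.1 referral concerns patients who have an antibody result and no symptoms. Testing prompted by symptoms is unlikely to find them, so the referral depends on a scheduled draw. On the 5-day schedule that draw comes after the last cycle, when the repeat exposure that the specialist might have advised on is already complete. Section 3.1 gives 5-day patients four cycles to show responsiveness. Section 2.1.2.10 excludes autoimmune disease but admits patients whose autoimmune event on prior ipilimumab has resolved.

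**Working it through.** **1. Where the marks fall.** The 5-day calendar has 13 schedule columns: Screening, Baseline, days 1 to 6, day 8, 21±4, End of Treatment, Follow-Up and End of Study. The 10-day calendar has 18.

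| Row | Marks after Baseline, 5-day | Marks after Baseline, 10-day |
|---|---|---|
| ANA, RF, anti-thyroid | End of Treatment | days 28-34 |
| Thyroid function | 21±4, End of Treatment | days 28-34 |

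Scheduled auto-antibody tests between first and last dose on the 5-day schedule: 0.

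**2. How far the 5-day calendar can be trusted.** The rows checked all have 13 cells. That shows equal length, not that the marks are right, so I compared rows with the text.

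- Agree: both flow cytometry rows are marked at 21±4, as their footnotes say ("Days 8 and 21 drawn with the routine laboratories"), and the PK row (days 1 to 6) matches 5.1.1.
- Disagree in part: anti-IL-15 antibodies are marked on day 1, at 21±4 and at Follow-Up. Section 5.1.4 also asks for day 6 and the off-treatment visit.
- Disagree: cytokines are marked on day 8 and at 21±4, yet footnote 12 takes them from PK tubes, and 5-day PK sampling ends on day 6.
- Disagree: vital signs are blank at 21±4, although footnote 6c says "Once at outpatient clinic follow-up visits on days 8 and 21".
- Disagree: imaging is blank at 21±4, although footnote 7 places it on days 14 to 21 of even cycles.

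Four rows conflict with the text. The auto-antibody blank may therefore be a slip. Unlike vital signs and imaging, its row has no footnote to supply the timing.

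**3. When the first scheduled result would come.** With 21-day cycles, cycle n starts on day 21(n−1)+1. The infusion ends 5 days later, and End of Treatment is 30 days after that:

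day = 21(n−1) + 1 + 5 + 30 = 36 + 21(n−1)

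Footnote 1 also allows "an additional 7 days allowed for reasons other than recovery for treatment-related toxicities". If every cycle uses it, the day is 36 + 28(n−1).

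| Cycles given | No delay | 7-day delay every cycle | Infusion days received |
|---|---|---|---|
| 1 | 36 | 36 | 5 |
| 2 | 57 | 64 | 10 |
| 3 | 78 | 92 | 15 |
| 4 | 99 | 120 | 20 |

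**4. What an in-cycle mark would gain.** The 21±4 window is days 17 to 25. With no delays, the first result comes 57−25 = 32 to 57−17 = 40 days earlier for a two-cycle patient, and 99−25 = 74 to 99−17 = 82 days earlier for a four-cycle patient. A one-cycle patient has no retreatment to inform.

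**5. How many patients are on this schedule.** Section 8 allows 3 to 6 evaluable patients at each of dose levels 7 and 8, and 9 at dose level 9: 3+3+9 = 15 to 6+6+9 = 21. Adding the 24 already enrolled and the 2 still to come reproduces the plan's totals: 24+2+15 = 41 and 24+2+21 = 47. Without the expansion, which the Schema makes conditional on a confirmed response, the range is 3×3 = 9 to 3×6 = 18. Both ranges assume that all three dose levels open. The number given two or more cycles is not stated.

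**The case against.** The strongest reply is that an End-of-Treatment-only mark proves little in this calendar. Imaging has exactly that mark after baseline, yet it is plainly done in-cycle. Section 3.6 says the panel belongs to every cycle, so a site might follow the text or raise a query. This stands as a reason for caution: the documents do not show that the sponsor meant to drop the test. But 3.6 defers to the calendar, and nothing else in the 5-day schedule gives an in-cycle time for this panel.

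A second reply takes the calendar at face value and calls the timing a design choice. That is possible, but it leaves a test on the on-therapy list with no on-therapy time point.

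A third reply is that no dosing decision turns on the result. This stands, and it sets the size of the point. The referral does not gate retreatment, and the vital-organ stopping rule rests on clinical evidence. TSH and T4 are marked at 21±4, examinations and chemistry continue, and 3.6.8 permits tests when clinically indicated.

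A reader might infer that auto-antibodies go unmonitored on the 5-day schedule, or that autoimmune toxicity would be missed. The documents do not support either reading. The panel is still scheduled at End of Treatment, so the referral is delayed rather than removed, and clinical detection is unaffected. Nor do they support applying day 99 to every 5-day patient: progression stops treatment earlier, and that figure needs four cycles.

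**Conclusion.** The inconsistency is real and minor. A site following the 5-day calendar has no scheduled auto-antibody test between cycles, and the referral for asymptomatic new auto-antibodies waits until about day 57 after two undelayed cycles or about day 99 after four. If every cycle used the 7-day allowance, those days would be 64 and 120. The figures assume 5-day infusions given in full and an End of Treatment visit 30 days after the last dose.

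Only patients given two or more cycles are affected. Nothing here bears on the DLT definition, the MTD or the response analysis. Confidence is medium, because the calendar conflicts with the text in other rows and the blank may be a drafting omission. The same correction is needed whether it was intended or not.

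**What to change.** In 3.8.2, add a mark for the ANA, RF and anti-thyroid panel in the 21±4 column, on the same draw as TSH and T4, and keep the End of Treatment mark.

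Do not require the draw on days 17 to 20. Footnote 1 says "Cycle 1 day 21 and cycle 2 day 1 maybe the same calendar day for certain patients", and for those patients an earlier draw could mean an extra visit. Draw before the next cycle only when the end-of-cycle visit already falls earlier in the ±4-day window. When the draw coincides with day 1 of the next cycle, its result informs only later cycles.

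The cost is one added serum panel per cycle on an existing draw: 1 to 4 per patient over the first four cycles, and at most 21×4 = 84 across 21 evaluable patients. Some referrals will follow non-specific positives. The documents give no rate. If 5% to 20% of 21 patients newly tested positive without disease (an assumption), that is 21×0.05 = 1.1 to 21×0.20 = 4.2, or about 1 to 4 patients.
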